## **CLINICAL TRIAL PROTOCOL SYNOPSIS**

Company name	Boehringer Ingelheim
Protocol date	22 October 2020
Revision date	10 May 2021
BI trial number	1450-0001
Title of trial	Safety, tolerability, pharmacokinetics, and pharmacodynamics of single rising intravenous doses of BI 765080 in healthy male subjects (single-blind, randomised, placebo-controlled, parallel-group design)
Principal Investigator	[REDACTED]
Trial site	[REDACTED]
Clinical phase	I
Trial rationale	In this first-in-human trial, the effects of single rising doses of BI 765080 on safety, tolerability, pharmacokinetics, and pharmacodynamics will be assessed as the basis for further development in patients with chronic kidney disease.
Trial objectives	To investigate safety, tolerability, pharmacokinetics, and pharmacodynamics following single rising intravenous doses of BI 765080
Trial endpoints	Primary endpoint to assess safety and tolerability of BI 765080 is the percentage of subjects with drug-related adverse events Secondary endpoints: 

– AUC0-∞ of BI 765080

– Cmax of BI 765080

Trial design	Single-blind, randomised within dose groups, placebo-controlled, parallel-group design
Number of subjects	
total entered	48*
each treatment	8 per dose group (6 on BI 765080 and 2 on placebo) * Additional subjects may be entered to allow testing of additional doses on the basis of experience gained during the trial conduct (e.g. preliminary PK data), provided the planned and approved highest dose will not be exceeded. Thus, the actual number of subjects entered may exceed 48, but is not to exceed 80.
Diagnosis	Not applicable

Proprietary confidential information © 2021 Boehringer Ingelheim International GmbH or one or more of its affiliated companies

Main criteria for inclusion	Healthy male subjects, age of 18 to 50 years (inclusive), body mass index (BMI) of 18.5 to 29.9 kg/m  (inclusive)
Test product	BI 765080 powder for solution for injection/infusion, 50 mg/vial
dose	Single doses of 1 mg, 10 mg, 25 mg, 50 mg, 100 mg, and 200 mg
mode of admin.	Intravenous as 30 min infusion
Comparator product	Matching placebo for BI 765080 concentrate for infusion solution
dose	Not applicable
mode of admin.	Intravenous as 30 min infusion
Duration of treatment	Single dose
Statistical methods	Descriptive statistics will be calculated for all endpoints.

Proprietary confidential information © 2021 Boehringer Ingelheim International GmbH or one or more of its affiliated companies

## FLOW CHART

Visit	Day	Planned time (relative to drug administration) [h:min]	Approximate clock time of actual day [h:min]	Event and comment	Safety laboratory	PK blood 	Body temperature	12-lead ECG	Continuous ECG monitoring	Vital signs (BP, PR)	Questioning for AEs and concomitant therapy 
1	-21 to -3			Screening (SCR) 	A		x	x		x	
2	-2	-48:00	08:00	Ambulatory visit 	B 		x			x	
	-1	-12:00	20:00	Admission to trial site	x 		x			x	
	1	-3:00	06:00	Allocation to treatment 	B 	x 	x 	x 	▲	x 	x 
		0:00	08:00	Drug administration start of infusion			x 			x	x 
		0:30	08:30	end of infusion		x	x 			x	x 
		1:00	09:00			x	x 			x	x
		1:30	09:30				x 			x	x
		2:00	10:00	light breakfast 		x	x 			x	x 
		3:00	11:00			x	x 			x	x
		4:00	12:00	lunch 	x 	x	x 	▼		x	x
		6:00	14:00			x	x 			x	x
		8:00	16:00	Snack (voluntary) 		x	x 			x	x
		10:00	18:00	Dinner 		x					
		12:00	20:00			x	x 			x	x
	2	24:00	08:00	Breakfast 	B 	x	x 			x	x
		34:00	18:00	Dinner 		x	x 			x	x
	3	48:00	08:00	Breakfast  discharge from trial site (confirmation of fitness  )		x	x 			x	x
	4	72:00	08:00	Ambulatory visit	B	x	x			x	x
	7	144:00	08:00	Ambulatory visit	B	x	x			x	
	14	312:00	08:00	Ambulatory visit		x	x			x	
	21	480:00	08:00	Ambulatory visit	B	x	x			x	
	28	648:00	08:00	Ambulatory visit		x	x			x	
	56	1320:00	08:00	Ambulatory visit	B	x 	x			x	
	84	1992:00	08:00	Ambulatory visit		x 	x			x	
3	84-87			End of trial (EoTrial) examination 	B		x	x		x	x

1. Subject must be informed and written informed consent obtained prior to starting any screening procedures. Screening procedures include physical examination, check of vital signs and body temperature, ECG, safety laboratory (including drug screening), demographics (including determination of body height, weight, smoking status, alcohol history, relevant medical history, concomitant therapy, and review of inclusion/exclusion criteria).
2. The time is approximate; procedures are to be performed and completed within the 3 h prior to drug administration. Allocation to treatment may be performed at any time following enrolment but must be completed prior to (first) drug administration.
3. If several actions are indicated at the same time, the intake of meals will be the last action.
4. At the end of trial visit the EoTrial examination includes physical examination, body weight, vital signs, ECG, safety laboratory, recording of AEs, and concomitant therapies. EOT to be performed not before last PK sampling.
5. Only urine drug screening and alcohol breath test will be done at this time.
6. AEs and concomitant therapies will be recorded throughout the trial, but will be specifically asked for at the times indicated in the [Flow Chart](#) above.

Proprietary confidential information © 2021 Boehringer Ingelheim International GmbH or one or more of its affiliated companies

7. Safety laboratory to be taken and to be medically evaluated within 3 days prior to administration of study drug; this safety laboratory assessment can be omitted if the screening examination is performed on Days -5 to Day -3.
8. The ECG recording has to be performed in triplicate ECGs at this time
9. Sampling times and periods may be adapted based on information obtained during the trial (e.g., due to preliminary PK data) including addition of samples and visits as long as the total blood volume removed does not exceed 500 mL per subject
10. At baseline (i.e. Day 1, prior to drug administration) 3 triplicate ECGs are recorded within approximately one hour. The recordings should be separated by at least 15 minutes.
11. In case blood levels still exceed LOQ, additional PK [REDACTED] samples may be collected beyond Day 28.

[figure not shown]
14. SARS-CoV-2 PCR test will be performed.
15. Confirmation of fitness includes physical examination.
16. Letters A and B describe different sets of safety laboratory examinations (see Section [5.2.3](#)).
17. Local tolerability inclusive.

## **ABBREVIATIONS**

ACE	Angiotensin-converting-enzyme
AE	Adverse event
AESI	Adverse events of special interest
ALCOA	Attributable, legible, contemporaneous, original, accurate
ALT	Alanine amino transferase
ARB	Angiotensin-receptor blocker
AST	Aspartate amino transferase
AUC	area under the concentration
AUC0-∞	Area under the concentration-time curve of the analyte in serum over the time interval from 0 extrapolated to infinity
BI	Boehringer Ingelheim
BMI	Body mass index (weight divided by height squared)
BP	Blood pressure
CA	Competent authority
CI	Confidence interval
CKD	Chronic kidney disease
Cmax	Maximum measured concentration of the analyte in serum
CML	Clinical Monitor Local
COVID-19	Corona virus disease 2019
CRF	Case Report Form, paper or electronic (sometimes referred to as 'eCRF')
CTM	Clinical Trial Manager

Proprietary confidential information © 2021 Boehringer Ingelheim International GmbH or one or more of its affiliated companies

CTP	Clinical trial protocol
CTR	Clinical trial report
DILI	Drug induced liver injury
DLT	Dose-limiting toxicity
ECG	Electrocardiogram
eCRF	Electronic case report form
eDC	Electronic data capture
EDTA	Ethylenediaminetetraacetic acid
EoTrial/EoT	End of trial
ESRD	End-stage renal disease
EudraCT	European Clinical Trials Database

FDA	Food and Drug Administration
-----	------------------------------

GCP	Good Clinical Practice
GFR	Glomerular filtration rate
HD	Hemodialysis
HIV	Human Immunodeficiency Virus
HR	Heart rate
HUVEC	Human umbilical vein endothelial cells
IB	Investigator's brochure
IEC	Independent Ethics Committee
iPD	Important protocol deviation
IRB	Institutional Review Board
ISF	Investigator site file
IUD	Intrauterine device
IUS	Intrauterine hormone-releasing system
i.v.	Intravenous

MDA	Methylenedioxymethamphetamine
MDMA	Methylenedioxymethamphetamine
MedDRA	Medical Dictionary for Regulatory Activities

MTD	Maximum tolerated dose
NKcell	Natural killer cell
NOAEL	No-observed-adverse-effect level
PCR	Polymerase chain reaction
PD	Pharmacodynamic(s)

Proprietary confidential information © 2021 Boehringer Ingelheim International GmbH or one or more of its affiliated companies

PK	Pharmacokinetic(s)
PKS	Pharmacokinetic parameter analysis set
PR	Pulse rate
QT	Time between start of the Q-wave and the end of the T-wave in an electrocardiogram
QTc	QT interval corrected for heart rate using the method of Fridericia (QTcF) or Bazett (QTcB)
Q2W	Every 2 weeks
Q3W	Every 3 weeks
REP	Residual effect period
RR	Respiratory rate
SAE	Serious adverse event
SCR	Screening
SGLT2	Sodium-glucose co-transporter-2
SOP	Standard operating procedure
SRD	Single-rising dose
TMDD	Target mediated drug disposition
TMF	Trial master file

TS Treated set

TSAP	Trial statistical analysis plan
ULN	Upper limit of normal

WFI	Water for Injection
WHO	World Health Organization
XTC	Ecstasy

## **1. INTRODUCTION**

BI 765080 is intended for the treatment of chronic kidney disease (CKD). This is the first trial in humans.

### **1.1 MEDICAL BACKGROUND**

The incidence and prevalence of CKD can vary as a result of the underlying aetiology [R19-0901]. Overall, around 12% of the general population in Europe has CKD stages 3–5 [R19-1388], with considerable variation across European countries, ranging from 4.1% to 25.5% [R19-1184]. In developed countries, CKD is generally associated with diabetes, hypertension, old age, obesity, and cardiovascular disease. Diabetic glomerulosclerosis and hypertensive nephrosclerosis are the presumed pathological entities; however, exact diagnosis is often difficult. It has been shown that both reduced GFR and increased albuminuria are independent predictors of mortality [R17-2621, R17-2619].

Current treatment of CKD is based on clinical diagnosis and staging of GFR decline and severity of albuminuria. The current standard of care is angiotensin-converting-enzyme (ACE) inhibitors and angiotensin-receptor blockers (ARBs) [P11-14681], usually in association with diuretic drugs in patients with high concentrations of albuminuria [R19-0901]. Selective nonsteroidal mineralo-corticoid receptor antagonists such as finerenone and sodium-glucose co-transporter-2 (SGLT2) inhibitors may be considered as standard of care in the future [P18-03010, R19-1139, R19-1356].

Proprietary confidential information © 2021 Boehringer Ingelheim International GmbH or one or more of its affiliated companies

Although ACE inhibitors and ARBs have demonstrated efficacy in slowing the progression of diabetic nephropathy, it should be acknowledged that the relative risk reduction was small (16% in RENAAL and 19% in IDNT) for the triple composite primary endpoint of all-cause death, ESRD, or doubling of serum creatinine [[R02-0327](#), [R02-2101](#)]. The residual risk is still considerably high. Therefore, there are high unmet needs for an effective and safe treatment that can further slow, halt, or reverse the progression of CKD.

## **1.2 DRUG PROFILE**

For a comprehensive description of the BI 765080 profile, please refer to the current Investigator's Brochure (IB) [[c30981435](#)].

### **1.2.1 Nonclinical pharmacology**

The core safety pharmacology (neurological, cardiovascular, and respiratory functions) was evaluated as part of the 4-week (rat) and 13-week (monkey) GLP repeat dose toxicity studies (see Section 1.2.2.3). [REDACTED]

### **1.2.2 Toxicology**

#### Rationale for Toxicology Species Selection

##### **1.2.2.1 Genotoxicity**

Genetic toxicity studies are generally not applicable to therapeutic antibodies, as they are not expected to interact directly with DNA. Therefore, genetic toxicity studies were not conducted per ICH S6 (R1): 'Preclinical Safety Evaluation of Biotechnology-derived Pharmaceuticals' [[R11-1428](#)].

[figure not shown]
Proprietary confidential information © 2021 Boehringer Ingelheim International GmbH or one or more of its affiliated companies

**1.2.2.2 Single dose toxicity**

[figure not shown]
No single-dose toxicity assessments have been conducted with BI 765080

[figure not shown]
**1.2.2.3 Repeated dose toxicity**

4-Week study in rats, GLP [[n00277285](#)]

13-Week study in cynomolgus monkeys, GLP [[n00277281](#)]

In summary, BI 765080 administered to monkeys intravenously once weekly for 13 consecutive weeks at [REDACTED] week was well tolerated in animals surviving until scheduled necropsy. [REDACTED]

Proprietary confidential information © 2021 Boehringer Ingelheim International GmbH or one or more of its affiliated companies

#### 1.2.2.4 Special studies

##### Local tolerance

There was no evidence of local BI 765080-related effects at the injection sites during the 4-week repeat dose toxicity study in rats [[n00277285](#)].

In the 13-week repeat dose toxicology study in monkeys [[n00277281](#)], one monkey given a [REDACTED] dose showed localized injection site reactions with clinical signs including swelling, exudate, and/or discharge at right and left cephalic vein dose sites.

#### **1.2.2.5 Reproductive and developmental toxicity**

Developmental and reproductive toxicity studies have not been conducted with BI 765080.

#### **1.2.2.6 Phototoxicity**

Therapeutic antibodies are not generally expected to be phototoxic unless related to the mechanism of action. Therefore, no phototoxicity studies were conducted. There were no toxicities in the skin or eyes related to light exposure observed in the repeat dose toxicity studies [[n00277285](#), [n00277281](#)].

### **1.2.3 Nonclinical pharmacokinetics**

#### **1.2.4 Prediction of human pharmacokinetics**

[REDACTED]

#### **1.2.5 Clinical experience in humans**

This will be the first clinical trial in humans with BI 765080.

[REDACTED]

### **1.2.6 Residual Effect Period**

The residual effect period (REP) of BI 765080, when measurable drug levels or PD effects are still likely to be present, is not known for this first-in-human trial. Conservatively, a minimum observation period of approximately 4-fold the estimated  $t_{1/2}$  has been selected. Therefore, the individual subject's end of trial is on Day 84-87 following dosing with investigational drug at the earliest (see [Flow Chart](#)).

### **1.2.7 Drug product**

BI 765080 is

### **1.3 RATIONALE FOR PERFORMING THE TRIAL**

BI 765080 is

In this first-in-human trial, the effects of single rising doses of BI 765080 on safety, tolerability, pharmacokinetics, and pharmacodynamics will be assessed as the basis for further development in patients with CKD.

Within each dose group, all actively treated individuals will receive the same BI 765080 dose. The next higher dose will only be administered to the next group if the treatment in the preceding dose group was safe and well tolerated (see Section [3.1](#)). The background for dose selection and escalation steps is described below.

#### **1.3.1 Starting dose**

The starting dose in healthy humans in this initial Phase I single-rising dose (SRD) trial is 1 mg (0.017 mg/kg).

### 1.3.2 Maximum dose and escalation

The following doses have been chosen for this trial: 1 mg, 10 mg, 25 mg, 50 mg, 100 mg and 200 mg. The selected doses are expected to cover the range of subtherapeutic, anticipated therapeutic, and supratherapeutic doses. The dose of 200 mg will allow for the collection of safety data in case higher doses are needed to assess efficacy in future clinical trials. Predictions based on preclinical testing may turn out to be too optimistic and higher doses/exposure may be required, i.e. 400 mg, maximal 600 mg. The dose higher than 200 mg will only occur if safety and tolerability of 200 mg support increasing the dose and 200 mg does not achieve the estimated exposure, which will be provided by substantial CTP amendment.

A dose of 200 mg is expected to be safe, since no adverse effects in rats or monkeys were associated with BI 765080 administration at dose levels up to 100 mg/kg (NOAEL; see Section 1.2). The planned maximum exposure in humans is predicted to be substantially lower than the exposures in the rat and monkey toxicity studies (Table 1.3.2: 1). The dose escalation up to and including the maximum dose will only occur if safety and tolerability of preceding dose levels support increasing the dose (see Section 3.1).

Table 1.3.2: 1 Planned maximum dose and estimated exposure multiples versus exposures in the rat and monkey

the *Journal of the American Statistical Association* (1980, 75, 311-322) and the *Journal of the Royal Statistical Society, Series B* (1981, 43, 1-37). The latter paper is the most comprehensive treatment of the topic, and it is the source of the following summary. The *Journal of the Royal Statistical Society, Series B* paper is available online at <http://www.jstor.org>.

## 1.4 BENEFIT - RISK ASSESSMENT

Participation in this clinical trial is without any (therapeutic) benefit for healthy subjects. Their participation, however, is of major importance for the development of a new therapy for CKD. Subjects are exposed to risks of study procedures and risks related to the exposure to the trial medication.

### 1.4.1 Procedure-related risks

The use of an indwelling venous catheter or venepuncture for e.g. blood sampling may result in mild bruising and, in rare cases, in transient inflammation of the wall of the vein, or nerve injury, potentially resulting in paraesthesia, reduced sensibility, and/or pain for an indefinite period.

Proprietary confidential information © 2021 Boehringer Ingelheim International GmbH or one or more of its affiliated companies

The total volume of blood drawn per subject during the entire study will not exceed the volume of a normal blood donation (500 mL). No health-related risk to healthy subjects is expected from withdrawal of this volume of blood.

#### 1.4.2 Drug-related risks and safety measures

Factors of risk may derive from particular knowledge or the lack thereof, regarding (1) the mode of action, (2) the nature of the target, (3) the relevance of animal models and/or (4) findings in non-clinical safety studies.

##### Mode of action and nature of the target

The mode of action of BI 765080 and nature of the target are described in Section [1.1](#).

##### Relevance of animal species and models

Rat and cynomolgus monkey are considered suitable species for the nonclinical safety profiling of BI 765080

##### Findings in non-clinical safety studies

The toxicity profile of BI 765080 has been assessed in repeat dose toxicity studies in rats and cynomolgus monkeys that included immunotoxicology and/or core safety pharmacology endpoints (cardiovascular, neurologic, and respiratory function),

No adverse findings were associated with BI 765080 administration at dose levels up to 100 mg/kg. The nonclinical safety package for BI 765080 supports clinical trials in humans with i.v. administration for up to 13 weeks. The potential for BI 765080 immunogenicity in humans is considered low.

##### Safety measures

[figure not shown]
The following safety measures will be applied in order to minimise the risk for healthy volunteers:

- Careful dose selection, as described in Section [1.3](#), with large safety margins up to the maximum dose, based on a sound preclinical data package including repeat dose toxicity studies in rats (4 weeks) and monkeys (13 weeks)
- The i.v. administration as 30 min infusion allows immediate discontinuation and the ability to adapt further drug administration should any safety concerns arise (please refer to Section [4.1.1](#))
- For safety reasons, each dose group is divided into 3 cohorts: on the first study day of each dose level, only 2 subjects will be treated: one will receive active treatment, the other subject will receive placebo. If BI 765080 treatment is safe and tolerated in this first cohort, 2 subjects on active will be treated in the second cohort no sooner than on

[figure not shown]
Proprietary confidential information © 2021 Boehringer Ingelheim International GmbH or one or more of its affiliated companies

the next day. The remaining 4 subjects (either active or placebo) are the third cohort and will be treated no sooner than after 2 days following the first cohort. This design ensures that there is a time interval of at least 1 day between the first and second active dose of each dose level, which covers the  $t_{max}$  of BI 765080 (end of infusion) and the period of highest risk / peak effect. If BI 765080 is safe and shows acceptable tolerability in the first two cohorts, the remaining third cohort of the respective dose level can be dosed as close as 10 minutes apart.

- Dose escalation will be shallow. In addition, a time interval of at least 14 days will be maintained between first administration of study drug in the actual dose level and first administration in the next dose level, which is expected to cover the period of highest risk / peak effect. The decision to proceed to the next dose will be based upon the safety and tolerability of the preceding dose. The next dose will only be given if no safety concerns arise in the previous dose group (i.e. no dose-limiting events occur) and if none of the pre-specified trial-specific stopping criteria are met (see Section [3.3.4](#)).
- Doses will only be escalated if previously approved by the Principal Investigator (or an authorised deputy) and the Clinical Trial Leader (or an authorised deputy) after in-depth analysis of all available safety data in a documented Safety Review (see Section [3.1](#))
- Extensive monitoring of ECG and vital signs is incorporated, with continuous ECG monitoring over 4 hours post dose to cover the anticipated period of highest drug exposure. As an additional measure, triplicate ECGs and repeated single 12-lead ECGs are scheduled in the further course of the study. The rationale for the intensified ECG monitoring is not an expected increased risk of BI 765080 mediated effects on cardiac repolarization. Rather, it has been implemented to collect thorough ECG data at an early point in clinical development to perform ECG interval assessment under drug. In general, for biologics, QT prolongation is not usually an issue (unless there are mechanistic effects with the antibody that can lead indirectly to ECG changes [\[R09-2768\]](#), which is not expected to be the case for BI 765080)
- Extensive safety laboratory testing will be performed
- At each dose level, the subjects will stay at the site for at least 48 hours following drug administration
- During in-house-confinement, the subjects will be under close medical observation and thoroughly monitored for both expected and unexpected adverse events

Proprietary confidential information © 2021 Boehringer Ingelheim International GmbH or one or more of its affiliated companies

Although rare, a potential for drug-induced liver injury (DILI) is under constant surveillance by sponsors and regulators. Therefore, this trial requires timely detection, evaluation, and follow-up of laboratory alterations in selected liver laboratory parameters to ensure subjects' safety; see also Section [5.2.6.1.4](#), adverse events of special interest.

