### 3. DESCRIPTION OF DESIGN AND TRIAL POPULATION

### 3.1 OVERALL TRIAL DESIGN AND PLAN

This single-rising dose trial is designed as single-blind, randomised within dose groups, and placebo-controlled within parallel dose groups.

It is planned to include a total of 48 healthy male subjects in the trial. The subjects will be assigned to 6 groups consisting of 8 subjects per group; the groups will be dosed sequentially (see Table 3.1: 1). The investigator (after consultation with the sponsor) is allowed to alter the scheduled dose groups (e.g., add low and/or intermediate dose groups) based on experience gained during the study (for instance, based on preliminary PK data), provided the planned and approved highest dose is not exceeded. Thus, the actual number of subjects entered may be more than 48, but is not to exceed 80. Such changes may be implemented via non-substantial CTP amendments.

Within each dose group, 6 subjects will receive BI 765080 and 2 will receive placebo. Only one dose is tested within each dose group. For safety reasons, each dose group will consist of 3 cohorts. The trial medication will be administered in the following order:

- Cohort 1: 1 subject on active treatment followed by 1 subject on placebo (in total 2 subjects)
- Cohort 2: 2 subjects on active treatment (in total 2 subjects)
- Cohort 3: randomised to 3 subjects on active treatment and 1 subject on placebo (in total 4 subjects)

Between cohort 1 and cohort 2 there will be a time interval of at least 1 day, which is expected to be sufficient to detect relevant acute effects of BI 765080. Cohort 1 and cohort 3 will be separated by at least 2 days. This design ensures that between first and second active dose of each dose level, there is a time interval of at least 1 day, which covers the  $t_{max}$  of BI 765080 (end of infusion) and the period of highest risk / peak effect. If BI 765080 was safe and showed acceptable tolerability in the first two cohorts, the remaining third cohort of the respective dose level could be dosed as close as 10 minutes apart.

The dose groups to be evaluated are outlined in Table 3.1: 1 below.

Table 3.1: 1 Dose groups

Dose Group	1	2	3	4	5	6
Dose (mg)	1	10	25	50	100	200
Number of subjects	8	8	8	8	8	8
Subjects receiving placebo	2	2	2	2	2	2
Subjects receiving BI 765080	6	6	6	6	6	6

Proprietary confidential information © 2021 Boehringer Ingelheim International GmbH or one or more of its affiliated companies

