The groups will be dosed consecutively in ascending order, and a time interval of at least 14 days will be maintained between the last drug administration to subjects in the previous dose group and the first drug administration to subjects in the subsequent dose group. The decision to treat the next dose group will be based upon safety and tolerability of all the preceding dose groups. Preliminary PK [REDACTED] assessments may be performed between dose groups (see Section [7.4](#)). The next dose group will only be treated if, in the opinion of the investigator, no safety concerns have arisen in the preceding dose groups (i.e. no dose-limiting events occurred), and if none of the pre-specified trial-specific stopping criteria have been met (refer to Section [3.3.4.1](#)).

A documented safety review must take place prior to each dose escalation. Furthermore, an unscheduled safety review meeting can be requested anytime by the Principal Investigator (or an authorised deputy) or the sponsor of the study (for instance, due to the occurrence of any unforeseen adverse events). Dose escalation will only be permitted if no safety concerns exist in the opinion of the Principal Investigator (or an authorised deputy) and the clinical trial leader (or an authorised deputy). In addition, at least data from 6 evaluable subjects per dose level need to be available for escalation to higher dose.

Although no formal Safety Review meeting will take place within a given dose group, safety will be continuously monitored during this trial, and an individual will only be dosed in the absence of any safety concern (i.e. no dose-limiting events occurred) and if none of the pre-specified trial-specific stopping criteria have been met (refer to Section [3.3.4.1](#)).

The minimum data up to at least 48 hours post dosing set for review consists of the following:

- AEs in the current and preceding dose groups, including clinically relevant findings from ancillary safety testing listed below (Note: AEs may be ongoing at the time of Safety Reviews and AE information may be subject to change prior to Database Lock)
- Results from 12-lead ECG and continuous ECG monitoring in the current and preceding dose groups based on assessment of the study site.
- Vital signs in the current and preceding dose groups
- Clinical laboratory tests in the current and preceding dose groups

- Check of criteria for stopping subject treatment as per Section [3.3.4.1](#)

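### Protocol Sections 1.4.2 and 3.1 start the 14-day minimum between dose levels from different doses, and the Section 3.1 escalation condition does not cite the section that holds the escalation-stopping rules

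*Protocol*

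**What the plan says.** **Interval between dose levels.** The safety measures in protocol Section 1.4.2 state that "a time interval of at least 14 days will be maintained between first administration of study drug in the actual dose level" and the first administration at the next level. The clock therefore runs from first dose to first dose. Section 3.1 states that "at least 14 days will be maintained between the last drug administration to subjects in the previous dose group" and the first administration in the following group. That clock runs from last dose to first dose. Both are minimums of 14 days.

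**Dosing within a group.** Each group of 8 is dosed in three cohorts. Section 3.1 says "Cohort 1 and cohort 3 will be separated by at least 2 days" and gives no maximum. The last cohort is described as "Cohort 3: randomised to 3 subjects on active treatment and 1 subject on placebo (in total 4 subjects", so it holds half of the 6 active subjects at that level.

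**Condition for treating the next group.** Section 1.4.2 allows the next dose only "if none of the pre-specified trial-specific stopping criteria are met (see Section"; the section it names is 3.3.4. Section 3.1 sets the same condition in its own words: "The next dose group will only be treated if, in the opinion of the investigator, no safety concerns have arisen". It adds that no trial-specific stopping criterion may have been met, and there it names Section 3.3.4.1.

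**What the cited sections hold.** Section 3.3.4.1 lists six reasons for an individual subject to discontinue treatment. Section 3.3.4.3 holds the rules that act on escalation. Item 2 ends it if more than half of the subjects at a level have qualifying adverse events, or on one drug-related serious event. Item 5 stops it on QT prolongation in at least 2 active subjects at a level. Item 6 is a group-level trigger on severe events.

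The SAP sections supplied do not address either point.

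**The concern.** These passages control when healthy volunteers receive the next higher dose in a first-in-human trial. Two sections of the same protocol give the same number of days with different starting points, and the protocol's own cohort spacing makes them differ. Someone who builds the dosing calendar from the list of safety measures could fix a date that the design section does not allow. The shorter observation time would fall on the last-dosed cohort.

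The reference matters for a similar reason. Someone checking whether the next group may be treated, and following the reference in Section 3.1, arrives at subject-level discontinuation reasons. The rules written to stop escalation sit two subsections further on.

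**Working it through.** **Inputs**
- Minimum interval: 14 days, first dose to first dose (Section 1.4.2).
- Minimum interval: 14 days, last dose to first dose (Section 3.1).
- d = days from the first to the last dosing within a group. Section 3.1 gives d of at least 2 and no maximum. Section 4.1.3 fills cohorts by subjects' availability, so d may exceed 2. Values above 2 in the table are assumptions.

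**Formulas**
- Section 1.4.2: the earliest next level is 14 days after the first dose, which is 14 − d days after the last dose.
- Section 3.1: the earliest next level is 14 days after the last dose, which is 14 + d days after the first dose.
- The two agree only if 14 − d = 14, that is d = 0, with the whole group dosed on one day. The cohort spacing excludes this.

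| d (days) | Basis | 1.4.2: days after last dose | 3.1: days after last dose | 1.4.2: days after first dose | 3.1: days after first dose |
|---|---|---|---|---|---|
| 2 | stated minimum | 14 − 2 = 12 | 14 | 14 | 14 + 2 = 16 |
| 3 | assumed | 11 | 14 | 14 | 17 |
| 5 | assumed | 9 | 14 | 14 | 19 |
| 7 | assumed | 7 | 14 | 14 | 21 |

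All entries are earliest permitted times, not planned dates. The earliest times differ by d days, so by at least 2.

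A schedule meeting Section 3.1 has a first-to-first interval of at least 14 + d, which exceeds 14, so it also meets Section 1.4.2. A schedule at the Section 1.4.2 minimum has a last-to-first interval of 14 − d, which is below 14, so it breaches Section 3.1.

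The flow chart gives a sense of scale. The Day 14 visit is at 312 h, and 312/24 = 13 days after dosing. At the Section 1.4.2 minimum with d = 2, cohort 3 is 12 days after dosing and has not reached that visit. This visit is not a stated condition for escalation; the minimum review data run to at least 48 hours.

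**The reference, side by side**
- Section 1.4.2 cites 3.3.4, the parent section, which contains both 3.3.4.1 and 3.3.4.3.
- Section 3.1 cites 3.3.4.1 only, in its visible text.
- Section 3.3.4.1 decides whether one subject stops treatment. Section 3.3.4.3, items 2 and 5, decides whether escalation stops.

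So the Section 3.1 reference does not reach the rules that match the condition it states.

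**Optional clarification: the denominator of item 2 in Section 3.3.4.3.** Item 5 names active subjects and item 6 names 8 subjects, but item 2 gives no count. The threshold is more than 50%.
- 4 of 6 active and 0 of 2 placebo affected: 4/6 = 66.7% (met) or 4/8 = 50.0% (not met).
- 3 of 6 active and 2 of 2 placebo affected: 3/6 = 50.0% (not met) or 5/8 = 62.5% (met).

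The reading can therefore change the result in either direction. The documents give no event rates, so no trigger probability is offered.

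**The case against.** **On the interval.** Both passages set floors, not dates. Section 1.4.2 permits a step at 12 days after the last dose but does not cause one, and following Section 3.1 satisfies both. Other text also sends the reader to Section 3.1. Section 1.3 allows the next dose only "if the treatment in the preceding dose group was safe and well tolerated (see Section", and the section named is 3.1. Section 1.4.2 allows escalation only "after in-depth analysis of all available safety data in a documented Safety Review", again with a reference to 3.1. This stands, and it limits the practical risk. It does not remove the contradiction, because Section 1.4.2 presents its interval as a measure to be applied and gives its own reason for it.

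**On the reference.** Section 3.3.4.1 is not only administrative. Items 4 and 5 cover blood pressure, ECG and liver criteria, and the Section 3.1 review list includes a check of that section. The reference may be meant as an additional check. Section 3.1 also requires that no dose-limiting events have occurred, and that both the Principal Investigator and the Clinical Trial Leader have no safety concerns. All of this stands, so the reference is best called incomplete.

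**Stronger readings that the documents do not support.** A reader might infer that escalation has no effective stopping rule. It has: items 2 and 5 of Section 3.3.4.3 are mandatory in their own wording and do not depend on being cited. A reader might infer that the Section 1.4.2 reference to 3.3.4 is also wrong. It is not, since 3.3.4 covers both subsections. A reader might add up the difference over all escalation steps. That sum measures calendar time and not safety, because each step concerns a different group. Parts of Section 3.1 and of its amendment description are redacted, so nothing is claimed beyond the visible text.

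**On item 2.** The unqualified phrase most naturally covers all 8 subjects, given that item 5 adds a restriction to active treatment and item 6 counts 8. This is why it is only an optional clarification.

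**Conclusion.** The protocol contradicts itself on the minimum interval between dose levels. At the shortest permitted spread of 2 days within a group, the Section 1.4.2 minimum allows the next level 12 days after the last dose, and Section 3.1 requires at least 14. For a longer spread d the first figure is 14 − d. Only d = 2 rests on the documents; larger values are assumed, and no maximum is stated. The documents do not show that any step would be taken at the shorter interval, only that one section permits it and the other does not.

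The reference in the Section 3.1 condition is incomplete: it leads to individual-subject discontinuation criteria and not to the rules that stop escalation. Those rules still bind, and no rule is lost.

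Both are internal inconsistencies in wording. The interval is the more important, because it is a numerical threshold for escalation in a first-in-human trial. Which anchor or rule should apply is for the sponsor.

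**What to change.** 1. Reconcile Sections 1.4.2 and 3.1 to one anchor for the 14-day interval. The sponsor decides which.
2. Reconcile the reference in the Section 3.1 condition for treating the next group with Section 3.3.4.3, which holds the escalation-stopping rules. If the check of Section 3.3.4.1 is intended as well, say so. The Section 1.4.2 reference to 3.3.4 needs no change on this account.
3. Optional: state whether item 2 of Section 3.3.4.3 counts all 8 subjects at a dose level or only the 6 active ones.

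The cost is protocol wording, with no new data, assessments or analyses, and no SAP change. Any effect on the calendar depends on the anchor chosen: the earliest start of the next level differs by d days between the two.
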